1.5. Risk/Benefit Assessment for the Study

The risk/benefit for this study is acceptable due to the following considerations: i) treatment of HCV is indicated and important in all HIV co-infected patients due to accelerated progression of liver disease; ii) 12 weeks of LDV/SOF provides high HCV SVR rates in HIV/HCV co-infected subjects; iii) changing ARV regimens is an accepted strategy for management of patients prior to initiation of HCV therapy (AASLD/ IDSA Guidelines); iv) changing to E/C/F/TAF from other ART has been shown to be safe, effective and have superior treatment outcome than maintaining a current suppressive regimen {Mills et al 2015}; v) F/R/TAF is bioequivalent to approved HIV regimens and achieves plasma concentrations of FTC, RPV and TAF that have proven to be safe, well tolerated and effective in maintaining virologic suppression in HIV-infected patients. Thus, for individual subjects there is benefit to treating their HCV and for all co-infected patients, finding safe, tolerable, efficacious and simple regimens will be a major advance in treatment.

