3.4. Duration of Treatment

The HIV treatment duration is from the Day 1 visit until the last study visit at the Post-HCV Treatment Week 12. The HCV treatment duration is 12 weeks. Screening assessments will be completed within 42 days of the Day 1 visit.

All subjects will complete the following study visits: Screening, Day 1, Weeks 4, 6 (laboratory visit only), 8 (start of HCV treatment), 12, 16, and 20 (end of HCV treatment), and post-HCV treatment visits 4 and 12 weeks after the last LDV/SOF dose.

Subjects who complete the study through the last study visit at the Post-HCV Treatment Week 12 visit will be required to return to the clinic 30 days after the completion of the study treatment for a 30-Day Follow-Up visit.

- a Following the Day 1 visit, subjects will return for study visits at Weeks 4, 6 (laboratory visit only), 8, 12, 16, 20, and Post-HCV Treatment 4 and 12 weeks after the last LDV/SOF dose.
- b Part 1: subjects are randomized to either E/C/F/TAF FDC or F/R/TAF FDC on Day 1 and maintain HIV treatment to the Week 8 visit.
- c Part 2: At Week 8, once HIV-1 RNA suppression (< 50 copies/mL) is confirmed (based on the Week 6 HIV-1 RNA value), subjects will start on LDV/SOF FDC for 12 weeks (until Week 20) while maintaining their HIV treatment. At Week 20, LDV/SOF FDC will be discontinued while continuing HIV treatment. Subjects will continue in the study for another 12 weeks to determine SVR4 (4 weeks post-HCV treatment) and SVR12 (12 weeks post-HCV treatment).

- d Subjects who complete the study through the Post-HCV Treatment Week 12 visit will be required to return to the clinic 30 days after the completion of the study treatment for a 30-Day Follow-Up Visit.
- e At the Day 1 visit, subjects will switch to either E/C/F/TAF FDC or F/R/TAF FDC and continue on HIV treatment until the last study visit at the Post-HCV Treatment Week 12 visit.

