5.4. Prior and Concomitant Medications

The use of medications for the treatment of HIV and HCV, other than the study treatments (ie, E/C/F/TAF, F/R/TAF, or LDV/SOF), is prohibited.

Should subjects have a need to initiate treatment with any excluded concomitant medication, the Gilead Medical Monitor must be consulted prior to initiation of the new medication. In instances where an excluded medication is initiated prior to discussion with the Medical Monitor, the Investigator must notify Gilead as soon as he/she is aware of the use of the excluded medication.

Concomitant medications taken within 30 days prior to the Screening visit and up to and including 30 days after the last dose of study drug need to be recorded in the source documents and electronic case report form(s) (eCRFs).

Medications listed in Table 5-1 (E/C/F/TAF + LDV/SOF) and Table 5-2 (F/R/TAF + LDV/SOF) and use of herbal/natural supplements are excluded or should be used with caution while subjects are participating in the study due to potential drug-drug interactions.

Drug Class	Agents Disallowed	Use With Caution	
Acid Reducing Agents Antacids ^a		Elvitegravir plasma concentrations are lower with antacids due to local complexation in the GI tract and not to changes in gastric pH. It is recommended to separate study drug and antacid administration by at least 2 hours.	
		Proton-Pump Inhibitors, H2-Receptor Antagonists, Antacids	
Alpha Adrenergic Receptor Antagonists	Alfuzosin		
Analgesics		Tramadol, Propoxyphene: Concentrations may increase with study drug(s); clinical monitoring is recommended.	
Antiarrhythmics	Amiodarone ^c , Quinadine	Flecainide Quinidine, Propafenone, Systemic Lidocaine, Mexiletine, Disopyramide: Concentrations may increase with study drug(s) resulting in a potential for cardiac arrhythmias; clinical and ECG monitoring is recommended.	
		Concentrations of clarithromycin and/or cobicistat may be altered when clarithromycin is coadministered with study drug(s).	
Antibacterials		Patients with CL_{cr} greater than or equal to 60 mL/min: No dose adjustment of clarithromycin is required.	
		Patients with CL_{cr} between 30 mL/min and 60 mL/min: The dose of clarithromycin should be reduced by 50%.	
		Concentrations of telithromycin and/or cobicistat may be increased when telithromycis in coadministered with study drug. Clinical monitoring is recommended upon coadministration with study drug.	

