Phosphodiesterase-5 Inhibitors	Sildenafil (for PAH)	Tadalafil: Caution should be exercised, including consideration of dose reduction, when coadministered for treatment of pulmonary arterial hypertension.	
		Erectile Dysfunction:	
		Sildenafil, Vardenafil, Tadalafil: It is recommended that a single dose of Sildenafil no more than 25 mg in 48 hours, Vardenafil no more than 2.5 mg in 72 hours, or Tadalafil no more than 10 mg in 72 hours be coadministered.	
Sedatives/Hypnotics	Orally administered Midazolam, Triazolam	Buspirone, Clorazepate, Diazepam, Estazolam, Flurazepam, Zolpidem: A dose decrease may be needed for these drugs. Clinical monitoring is recommended.	

a It is recommended to separate antacid and LDV/SOF administration by 4 hours. H2-receptor antagonists may be administered simultaneously with or staggered from LDV/SOF at a dose that does not exceed doses comparable to famotidine 40 mg twice daily. Proton-pump inhibitor doses comparable to omeprazole 20 mg can be administered simultaneously with study drugs. Proton-pump inhibitors should not be taken before study drugs.

b May result in a decrease in the concentrations of study drugs.

c May result in symptomatic bradycardia. Mechanism is currently unknown. The use of amiodarone is prohibited from 60 days prior to Day 1 through the end of treatment

e Use with study drug may result in an increase in the concentration of rosuvastatin, which is associated with increased risk of myopathy including rhabdomyolysis

d Coadministration of E/C/F/TAF or LDV/SOF with digoxin may increase the concentration of digoxin. Caution is warranted and therapeutic concentration monitoring of digoxin is recommended when coadministered with E/C/F/TAF or LDV/SOF.

Drug Class	Agents Disallowed	Use With Caution
Acid Reducing Agents ^a	Proton pump inhibitors, such as Esomeprazole, Lansoprazole, Omeprazole, Pantoprazole, Rabeprazole	H2-Receptor Antagonists, Antacids Cimetidine, Famotidine, Nizatidine, Ranitidine Coadministration of H2-receptor antagonists (H2RA) may cause significant decreases in RPV plasma concentrations (increase in gastric pH). H2RAs should only be administered at least 12 hours before or at least 4 hours after F/R/TAF

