Alkaline antacids: antacids (eg, aluminum or magnesium hydroxide, calcium carbonate)		Antacids should be used with caution as coadministration may cause significant decreases in RPV plasma concentrations (increase in gastric pH). Antacids should only be administered either at least 2 hours before or at least 4 hours after F/R/TAF.
Antiarrhythmics	Amiodarone ^c , Quinidine	
Anticonvulsants ^b	Carbamazepine, Oxcarbazepine, Phenobarbital, Phenytoin	
Antifungals		Fluconazole, Itraconazole, Ketoconazole, Posaconazole, Voriconazole: may increase concentration of RPV.
Antimycobacterials ^b	Rifapentine, Rifabutin, Rifampin	
Cardiac Medications		Digoxin ^d
Corticosteroids: Systemic	Dexamethasone (more than a single dose)	
Herbal/Natural Supplements ^b	St. John's Wort, Echinacea, Milk thistle (ie, silymarin), Chinese herb Sho-Saiko-To (or Xiao-Shai-Hu-Tang)	
HMG-CoA Reductase Inhibitors ^e	Rosuvastatin	
Narcotic analgesics		Methadone Clinical monitoring is recommended as methadone maintenance therapy may need to be adjusted in some patients upon coadministration with RPV

	Table 5-2.	Prior and Concomitant Medications – F/R/TAF + LDV/SOF
--	------------	---

a It is recommended to separate antacid and LDV/SOF administration by 4 hours. H2-receptor antagonists may be administered simultaneously with or staggered from LDV/SOF at a dose that does not exceed doses comparable to famotidine 40 mg twice daily. Proton-pump inhibitor doses comparable to omeprazole 20 mg can be administered simultaneously with study drugs. Proton-pump inhibitors should not be taken before study drugs.

b May result in a decrease in the concentrations of study drugs.

c May result in symptomatic bradycardia. Mechanism is currently unknown. The use of amiodarone is prohibited from 60 days prior to Day 1 through the end of treatment

d Coadministration of F/R/TAF or LDV/SOF with digoxin may increase the concentration of digoxin. Caution is warranted and therapeutic concentration monitoring of digoxin is recommended when co-administered with F/R/TAF or LDV/SOF.

e Use with study drug may result in an increase in the concentration of rosuvastatin, which is associated with increased risk of myopathy including rhabdomyolysis.

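### Protocol Table 5-2 bans proton pump inhibitors with F/R/TAF, but footnote a on the same row permits doses comparable to omeprazole 20 mg with study drugs

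*Protocol*

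**What the plan says.** Three tables in the protocol govern acid-reducing drugs.

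- **Table 4-2** (Section 4.3, exclusion criterion 19) disallows PPIs. Its footnote a extends the list to all three study products. Its footnote b runs the ban from at least 42 days before Day 1 to the end of the study.
- **Table 5-1** (Section 5.4, E/C/F/TAF + LDV/SOF) names no disallowed acid reducer and puts PPIs in the caution column.
- **Table 5-2** (Section 5.4, F/R/TAF + LDV/SOF) has this entry in the disallowed column of its acid-reducer row: "Proton pump inhibitors, such as Esomeprazole, Lansoprazole, Omeprazole, Pantoprazole, Rabeprazole". In the caution column of that row, H2-receptor antagonists (H2RAs) are said to be capable of significantly lowering RPV concentrations through higher gastric pH, and a timing limit follows: "H2RAs should only be administered at least 12 hours before or at least 4 hours after F/R/TAF".

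The acid-reducer row of Table 5-2 carries superscript a. Footnote a has one sentence on antacids and one on H2RAs, both naming LDV/SOF. It then has two sentences on PPIs, neither of which names LDV/SOF: "Proton-pump inhibitor doses comparable to omeprazole 20 mg can be administered simultaneously with study drugs" and "Proton-pump inhibitors should not be taken before study drugs". Table 5-1 footnote a has the same text.

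**The concern.** The table cell and its footnote give opposite instructions for the same drug class, on the same row and for the same subjects. The permission is also the less safe of the two. On this row H2RAs are allowed only if kept well apart from F/R/TAF, and PPIs are the only class barred outright. Yet the footnote allows a PPI at the same time as study drugs.

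HIV control in the F/R/TAF arm is at stake. Section 1.5 justifies this regimen partly because it "achieves plasma concentrations of FTC, RPV and TAF that have proven to be safe, well tolerated and effective in maintaining virologic suppression". A subject whose RPV exposure falls loses some of that assurance. Under Section 6.9.1, confirmed rebound in Part 1 ends participation before LDV/SOF is started, and documented resistance in Part 2 ends the HIV study drug.

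**Working it through.** The plan states no figure on this point, so the check is a comparison of texts.

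**1. PPI status by location**

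| Place | Applies to | PPI status |
|---|---|---|
| Table 4-2 with footnotes a and b | All study drugs, whole study | Disallowed |
| Table 5-1, row | E/C/F/TAF + LDV/SOF | Caution |
| Table 5-1, footnote a | E/C/F/TAF + LDV/SOF | Allowed at doses comparable to omeprazole 20 mg |
| Table 5-2, row | F/R/TAF + LDV/SOF | Disallowed |
| Table 5-2, footnote a | F/R/TAF + LDV/SOF | Allowed at doses comparable to omeprazole 20 mg |

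Table 5-1 agrees with its own footnote. Table 5-2 does not. Separately, Table 4-2 conflicts with Table 5-1.

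**2. What the term study drugs covers.** The opening of Section 5.4 lists the study treatments as E/C/F/TAF, F/R/TAF and LDV/SOF. Table 4-2 footnote c says that certain anticonvulsants, antimycobacterials and herbal products may lower all HIV and HCV study drugs. Table 5-2 footnote b covers the same classes and shortens this to study drugs. The term therefore includes the HIV regimen. Footnote a itself names LDV/SOF when it means only LDV/SOF.

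**3. Whether row and footnote can both be obeyed.** For antacids and H2RAs they can: the footnote sets timing or dose around LDV/SOF, the table sets timing around F/R/TAF, and one dosing schedule can satisfy both. For PPIs they cannot, because the row leaves no permitted dose or time.

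**4. Whether an LDV/SOF-only reading would resolve it.** HIV study drug is planned for 8 + 12 + 12 = 32 weeks. LDV/SOF occupies Weeks 8 to 20, wholly inside that period, and subjects "continue on HIV treatment until the last study visit at the Post-HCV Treatment Week 12 visit". Unless the HIV study drug has been stopped and replaced under Section 6.5.1, a subject given a PPI with LDV/SOF is also taking RPV that day.

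**5. Likely origin.** Footnote d was adapted between Tables 5-1 and 5-2: the HIV product name changes. Footnote a was carried across unchanged. In Table 5-1 it fits, since that table attributes the antacid effect on elvitegravir to local binding and not to gastric pH.

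**6. Who could be affected.** PPIs are stopped at least 42 days before Day 1, so only F/R/TAF subjects who start or resume one on study matter. The ceiling is the planned arm of 60 over 32 weeks. The relevant number is smaller: those given a PPI because a site followed the footnote over the ban. The documents give no rate for it.

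**The case against.** The ban is explicit and appears twice: the Table 5-2 cell names omeprazole, and Table 4-2 covers the whole study. A site must overlook both to act on the footnote. The footnote also caps the dose, so it is not a general licence for PPIs.

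There are safeguards. Before an excluded drug is started, "the Gilead Medical Monitor must be consulted prior to initiation of the new medication". Concomitant medications are reviewed at every visit except the Week 6 laboratory visit. Exclusion criterion 19 refers investigators to the RPV prescribing information. SAP Section 7.4.2 summarises non-ARV concomitant medications by drug class and lists the subjects taking them, so PPI use would be visible in the planned output.

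Most of this stands, and it makes harm less likely. It does not reconcile the two instructions. The consultation rule is triggered by an excluded drug, and a site relying on the footnote may not regard a low-dose PPI as excluded. Medication review and HIV-1 RNA testing act after the drug has been taken. Scheduled HIV-1 RNA gaps are 2 to 4 weeks up to Post-HCV Treatment Week 4, then 8 weeks to Post-HCV Treatment Week 12.

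A reader might also infer that the Table 4-2 and Table 5-1 mismatch is a second safety problem. The documents do not support that: they describe no harm from limited PPI use with E/C/F/TAF. Because Table 4-2 is applied before the arm is known, the mismatch may be editorial. It is still real, since footnote b continues the ban on study.

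**Conclusion.** The point holds for Table 5-2. Footnote a is wrong as written and errs in the unsafe direction for the F/R/TAF arm. The contradiction needs no assumption. The harm rests on one inference: the protocol gives the gastric pH warning for H2RAs and antacids, not for PPIs, and I extend it to PPIs because they sit on the same row and are the only class disallowed there.

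The size of any effect on HIV outcomes cannot be derived from the documents. A reader might put a count on it. If 5% to 20% of the arm started a PPI, that would be 0.05 × 60 = 3 to 0.20 × 60 = 12 subjects. That rate is an assumption without a source in the documents, and the count would include subjects who would have taken a PPI whatever the footnote said. It does not measure the defect.

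A reader might also infer that the trial's main result is compromised. Nothing in the documents supports this. The one-sample SVR12 test, its power and the sample size do not depend on the footnote.

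The E/C/F/TAF mismatch is minor. It leaves unclear whether on-study PPI use in that arm is a deviation, and no planned analysis uses that status.

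**What to change.** Delete both PPI sentences from Table 5-2 footnote a, leaving the antacid and H2RA sentences. Replacing study drugs with LDV/SOF would not be enough, for the reason in step 4 of the working.

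For the minor point, the sponsor should state in Tables 4-2 and 5-1 whether PPIs are allowed with E/C/F/TAF after randomization. The documents do not show whether the stricter or the looser rule was intended, so the choice is the sponsor's.

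The cost is low: a short protocol amendment and a notice to approximately 50 centers. Section 9.2.1 requires IRB/IEC approval before a modification is implemented, so a site memo alone does not amend the text. Sections 9.1.2 and 9.2.1 make an exception for changes that reduce immediate risk to subjects. Design, sample size and analysis stay as they are.

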5.5. Accountability for Investigational Medicinal Product (IMP)

The investigator is responsible for ensuring adequate accountability of all used and unused IMP. This includes acknowledgement of receipt of each shipment of IMP (quantity and condition). All used and unused IMP dispensed to subjects must be returned to the site.

IMP accountability records will be provided by Gilead Sciences (or equivalent documentation maintained by the study site) to:

- Record the date received and quantity of IMP bottles
- Record the date, subject number, subject initials, the IMP bottle number dispensed
- Record the date, quantity of used and unused IMP returned, along with the initials of the person recording the information.

5.5.1. Investigational Medicinal Product Return or Disposal

IMP return and disposal will be performed as outlined in Section 9.1.7.

6. STUDY PROCEDURES

The study procedures to be conducted for each subject enrolled in the study are presented in tabular form in Appendix 2 and described in the text that follows. Additional information is provided in the study procedures manual.

The investigator must document any deviation from protocol procedures and notify Gilead or contract research organization (CRO).

6.1. Subject Enrollment and Treatment Assignment

It is the responsibility of the Investigator to ensure that each subject is eligible for the study before enrollment. Please refer to Section 5.1 for details about randomization and treatment assignment.

6.2. Pretreatment Assessments

6.2.1. Screening Visit

Subjects will be screened within 42 days prior to the Day 1 visit to determine eligibility for participation in the study. The following assessments will be completed and documented at screening:

- Obtain written informed consent
- Determine eligibility including cirrhosis determination (see Section 4.2 for details)
 - If the presence of cirrhosis is determined, then appropriate diagnostic imaging (CT or Ultrasound) should be performed within 6 months prior to Day 1 to exclude the presence of hepatocellular carcinoma
- Obtain medical history, including:
 - History of HIV-1 disease-related events and prior medications within 30 days of the Screening visit. For subjects with 3 or more prior ARV regimens, a regimen history should be provided for approval by the Sponsor.
 - Collection of historical HIV genotype, if available. If a historical genotype prior to first ARV is not available or subject had 3 or more prior ARV regimens, subject will have proviral genotype analysis for archived resistance prior to Day 1 (all proviral genotype reports must be reviewed and approved by Sponsor).

- If HCV treatment-experienced, record the duration of the prior treatment and the type of IFN +/- RBV + HCV PI administered. Record whether the subject had a Non-Response or Relapse/Breakthrough during prior treatment or was Treatment Intolerant.
 - Non-Response: Subject did not achieve undetectable HCV RNA while on treatment.
 - Relapse/Breakthrough: Subject achieved undetectable HCV RNA during treatment or within 4 weeks of the end of treatment, but did not achieve SVR
 - Treatment Intolerant: Subject discontinued HCV treatment of a regimen containing IFN either with or without RBV due to toxicity
- Complete physical examination (urogenital/anorectal exams will be performed at the discretion of the Investigator)
- Obtain vital signs measurement (blood pressure, pulse, respiration rate, and temperature)
- Obtain 12-lead ECG (performed supine)
- Obtain height and weight
- Obtain urine samples for the following laboratory analyses:
 - Urinalysis and urine chemistry
- Obtain blood samples for the following laboratory analyses:
 - Serum pregnancy test (females of childbearing potential only). If the test is positive, the subject will not be enrolled.
 - Chemistry profile: alkaline phosphatase, AST, ALT, total bilirubin, direct and indirect bilirubin, total protein, albumin, bicarbonate, BUN, calcium, chloride, creatinine, glucose, phosphorus, magnesium, potassium, sodium, and uric acid.
 - Hematology profile: complete blood count (CBC) with differential and platelet count
 - Coagulation assessments: International Normalized Ratio (INR), prothrombin time (PT), and activated partial thromboplastin time (APTT)
 - CD4+ cell count
 - Plasma HIV-1 RNA (COBAS[®] TaqMan[®] HIV RNA Test, v2.0)
 - Whole blood sample for HIV proviral genotype analysis of archived resistance (if a historical genotype prior to first ARV is not available or subject had 3 or more prior ARV regimens)
 - Plasma HCV RNA (COBAS[®] TaqMan[®] HCV Quantitative Test, v2.0)

- HCV genotype and subtype, and IL28B genotype testing
- Serology for:
 - HIV antibody
 - HBV core antibody (HBcAb), surface antibody (HBsAb), surface antigen (HBsAg), e-antibody (HBeAg), e-antibody (HBeAb), and HBV DNA
 - HCV antibody
- Obtain estimated glomerular filtration rate according to the Cockcroft-Gault formula (see Section 4.2 for details)
- Obtain details of adverse events related to screening procedures
- Review concomitant medications

Subjects meeting all of the inclusion criteria and none of the exclusion criteria will return to the clinic within 42 days after the Screening visit for the Day 1 assessments.

From the time of obtaining informed consent through the first administration of investigational medicinal product, record all serious adverse events (SAEs), as well as any adverse events (AE) related to protocol-mandated procedures on the adverse events electronic case report form (eCRF). All other untoward medical occurrences observed until dosing of study drugs, including exacerbation or changes in medical history are to be captured on the medical history eCRF. See Section 7, Adverse Events and Toxicity Management, for additional details.

